Study Protocol and Statistical Analysis Plan

Title: Effects of an exercise program for people with diabetic foot ulcers: A feasibility study with outcomes

Registration number: NCT03002155

Document date: Updated 2022-07-07

Aim of study:

This research aimed to address the concerning cycle of deconditioning and disablement in people with DFUs by introducing a seated exercise intervention to improve meaningful health and quality of life outcomes. We examined the feasibility of conducting a randomized controlled trial to assess the effects of 12-weeks of seated exercise in people with DFUs compared to peers who did not exercise. We also assessed physical, physiological, and psychosocial health outcomes in both groups. The exercise intervention in this study was EnhanceFitness,¹ an community-based group exercise program appropriate for people with weight-bearing restrictions due to wound-healing protocols. Numerous studies have been conducted that provide evidence of health benefits associated with participation in EnhanceFitness in older adults, including participants with diabetes.²⁻⁷ We hypothesized that people with DFU who engaged in the fitness program would report high levels of satisfaction, adherence and participation, and a low frequency of adverse events. We also hypothesized that participation in the exercise program would be associated with improvements in key health outcomes as compared to a standard-care control group, who were instructed not to engage in regular exercise (i.e., not to change their current habit of no regular exercise).

Materials and methods

A pilot randomized controlled trial was conducted. Study participants were randomly assigned to a group-based exercise program with a seated option for participation (the EnhanceFitness intervention, described below) or to the control group. Participants in the exercise group attended fitness classes for a 12-week period; those in the control group received standard care, which did

not include exercise. Both groups of participants were assessed at two time points, baseline and 12-week follow-up.

Participants

Participants (target n=40) were enrolled and randomly assigned to either the intervention or control group. A randomization schedule was created using random number generator in Microsoft Excel (Microsoft Corporation, Redmond, USA). The study research coordinator created the randomization schedule for 40 potential participants prior to any study enrollment. Group assignment was placed in sealed envelopes to blind study investigators to randomization allocation. Corresponding envelopes were not opened until the participant was enrolled into the study.

Eligibility criteria for this study included: (1) 18 or more years of age, (2) diagnosis of diabetes, (3) current or recently-healed DFU (in the last six months), (4) and able to attend regular exercise classes and two data collection sessions. Exclusion criteria included: (1) medical conditions where aerobic or resistance exercise was contraindicated⁸ (e.g., uncontrolled cardiovascular problems), (2) a score of less than 18 on the Montreal Cognitive Assessment indicating moderate cognitive impairment,⁹ (3) response from primary physician requesting that the participant not engage in exercise, (4) current participation in a regular exercise program (more than 30 minutes, more than 2 times a week).

Study participants were recruited from podiatry and wound care clinics in the metro area using posted recruitment materials. Potential participants were also identified through targeted

mailings to patients in the University of Washington medical system with ICD-10 codes that indicate the presence of a DFU. Interested patients were screened by telephone for initial eligibility and, if eligible to participate, were enrolled and randomized to either the exercise group or the control group. For those randomized to the exercise group, we sent a letter to each participant's primary physician to inform them of participation in the EnhanceFitness program. Physicians were asked to respond if their patient should not engage in moderate, non-weight bearing exercise. Informed consent was obtained from all participants prior to their involvement in the study.

Outcomes

Feasibility Outcomes. We assessed feasibility outcomes to inform future, large-scale RCT research in this area. The feasibility of conducting a RCT to assess effects of seated exercise in people with DFUs was evaluated using the following parameters: (1) recruitment and retention; (2) adherence to the exercise protocol; (3) participant satisfaction with the exercise program; and (4) presence of serious adverse events. Retention was quantified as the percent of participants that completed the study (i.e., attended both the baseline and 12-week follow up appointments), as well as percent of those who withdrew during the study or were lost to follow-up in each arm. Adherence was quantified as percent of exercise sessions attended by those randomized to the exercise group (out of 36 possible sessions). Satisfaction with EnhanceFitness was quantified as a continuous score on a measure of satisfaction, ranging from 0 (not at all satisfied) to 5 (very satisfied). Finally, presence of serious adverse events (SAEs: adverse outcomes, related or unrelated to the study, such as hospitalizations, emergency room visits, increase in wound size,

and infection, over the course of the study) was quantified as the total number of SAEs reported by participants in each trial arm.

Health Outcomes. We anticipated that exercise might affect many aspects of health and health-related quality of life in people with current or recently-healed DFUs. The following health outcomes were assessed: (1) glycated hemoglobin (HbA1c¹⁰); Five-times sit-to-stand test (5xSTS, a measure of lower extremity strength¹¹); Timed-up-and-go (TUG, a measure of functional mobility¹²); and 30-second biceps curls (a measure of upper extremity strength). We also asked participants to complete a survey comprised of standardized self-reported health measures, including the Patient-reported Outcome Measurement Information System measures of global health (PROMIS-Global 10-item short form),¹³ depression (PROMIS-Depression 4-item short form),¹⁴ fatigue (PROMIS-Fatigue 8-item short form), and physical function (PROMIS-Physical Function 11-item short form).¹⁵ The Activities-Specific Balance Confidence Scale was used to assess balance confidence.¹⁶

Additional variables. Participant characteristics (e.g., age, sex, body-mass index, duration of diabetes) were collected at baseline to characterize the sample and evaluate the comparability between the exercise and control groups.

Procedures

Participants were asked to come to the University of Washington for two data collection sessions. All study procedures were reviewed and approved by a University of Washington institutional review board (IRB). The study was also registered with clinicaltrials.gov

(registration number NCT03002155). Participants were compensated for their time and participation in the study.

Exercise intervention. EnhanceFitness, an existing, evidence-based exercise program, was the intervention for this study. These group classes were offered at no cost to participants. EnhanceFitness classes were designed specifically for older adults at all fitness levels and may be performed in a seated position. Classes were offered at multiple locations across the Seattle metropolitan region, including community and senior centers, making them a convenient option for participants in the study. Each hour-long EnhanceFitness class incorporated cardiovascular exercise (20 minutes), strength training (20 minutes), and stretching (10 minutes). Evidence suggests that EnhanceFitness improves strength,⁷ and reduces depression³ and falls⁵ in older adults. Participants in the exercise group attended EnhanceFitness classes three times a week for 12 weeks and were contacted regularly to remind them to attend their classes.

Control. Participants in the control group were contacted regularly to remind them to not change their exercise habits (self-reported as less than 30 minutes of activity, less than 2 times a week) while enrolled in the study. They were asked not to start new exercise regimens, or begin a regular exercise program. Any changes in their exercise routines were noted by researchers.

Baseline data collection session. At the baseline session, a study investigator explained the study to participants and obtained informed consent. We then administered a baseline survey and obtained performance measurements. The baseline survey included all self-reported health outcomes as well as demographic and health questions. Following the baseline survey, we

administered the 5xSTS, TUG, and biceps curls to assess each participant's baseline strength and mobility. At the end of the session, participants went to a hospital-based laboratory to have their blood drawn to test for HbA1c.

12-week data collection session. At the 12-week session, we administered a follow-up survey to assess changes in the previously listed self-reported health outcomes. The survey also included questions to assess satisfaction with the EnhanceFitness intervention for participants in the exercise group. Following the survey, we asked participants to perform the 5xSTS, TUG, and biceps curls. At the end of the session, the participant returned to the laboratory to have their blood drawn and tested for HbA1c.

Analysis

Sample Characteristics. Descriptive statistics (mean, standard deviation, frequency distributions) were calculated for variables used to characterize the sample (e.g., participant characteristics). Student *t*-tests (numeric data) and Chi-square tests (nominal data) were used to compare the intervention and control groups based on participant characteristics. The alpha level for these tests was set at $\alpha=0.05$ and significant findings for sample variables indicate that there are differences in demographic or clinical characteristics (e.g., age, sex, duration of diabetes) between the exercise and control groups.

Feasibility Outcomes. The ability to meet recruitment targets (20 participants per group, 40 total) was assessed. Retention (or percent of participants that completed the study) and percent attrition was calculated and reported separately for the intervention and control groups. Pre-intervention

characteristics were compared between participants who did and did not complete the study to determine if there was a biasing effect. Adherence to the protocol was assessed in the intervention group to quantify the extent to which participants attended exercise classes. Satisfaction with EnhanceFitness was assessed in the intervention group to ensure that participants reported a minimum of 4 on a 5-scale measure of satisfaction with the exercise intervention.

Health Outcomes. Descriptive statistics were calculated for all physical, physiological, and psychosocial outcomes. Separate repeated measures analyses of variance (ANOVA) were performed for each health outcome. The ANOVA models included two factors, each with two levels (group: intervention, control; time: pre-intervention, post-intervention). The alpha level was set at $\alpha=0.10$ for health outcomes and was not adjusted for multiple comparisons. A less conservative statistical approach is warranted for this pilot study so that effects of the intervention could be recognized and, if results suggested that the intervention was beneficial, the results could be used to power and inform a larger RCT. Significant interactions of group x time (with corresponding evidence of improved outcomes in the intervention group) would indicate that the exercise program improved physical, physiological, and psychosocial outcomes in the exercise group compared to the control group.

References

8. Dugan JA. Exercise recommendations for patients with type 2 diabetes. *Jaapa*. 2016;29(1):13-8.

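### The safety hypothesis is about adverse events, but the only safety outcome is a self-reported count of loosely defined serious events that names neither a new or reopened ulcer nor the usual exercise harms

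*Combined protocol and SAP*

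**What the plan says.** The Aim of study states the safety hypothesis: people with a diabetic foot ulcer who take part in the program "would report high levels of satisfaction, adherence and participation, and a low frequency of adverse events". It is not restricted to serious events.

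Under Outcomes (Feasibility Outcomes), the fourth and only safety parameter is serious adverse events. They are defined as "adverse outcomes, related or unrelated to the study, such as hospitalizations, emergency room visits, increase in wound size", with infection as the last example. The measure "was quantified as the total number of SAEs reported by participants in each trial arm".

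The eligibility criteria under Participants admit people with a "current or recently-healed DFU (in the last six months", so some may enter with no open wound.

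On timing, "Both groups of participants were assessed at two time points, baseline and 12-week follow-up". Under Procedures, the two sessions consist of surveys, three performance tests and a blood draw. Both arms also receive regular contacts: reminders to attend class in one arm, and reminders not to change exercise habits in the other. No adverse event questions, foot examination or wound measurement are described. The feasibility part of the Analysis section deals with recruitment, retention, adherence and satisfaction, and does not mention adverse events.

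**The concern.** The hypothesis and the outcome do not cover the same events. A trial meant to inform a larger one needs to know about events that bear on whether this group can exercise: a fall, a low blood sugar episode, an injury or pain that limits activity. None is named. Falls stand out, because the plan cites evidence that the program reduces falls and measures balance confidence, yet does not say that falls are recorded.

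The wound examples have a similar gap. Wound enlargement describes someone who already has a wound. For someone who enters healed, the corresponding foot event would be a new or reopened ulcer, and the list does not name it. That is an inference from the eligibility criteria, not a statement in the documents.

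At stake is what the trial can say about safety. A low count of self-reported serious events could be presented as support for a low frequency of adverse events when other events were never asked about. Capture could also differ by arm: exercisers are in class three times a week, the regular contacts serve different purposes in each arm, and participants can be expected to know which arm they are in.

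**Working it through.** The plan states no adverse event rate, no threshold for low and no safety sample size, so there is no figure to reproduce. The check is mainly one of text, with three illustrations of scale.

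**Text, side by side**

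| Element | Where | Scope |
|---|---|---|
| Hypothesis | Aim of study | Adverse events, without restriction |
| Outcome label | Outcomes, Feasibility Outcomes | Serious adverse events |
| Outcome definition | Same paragraph | Adverse outcomes, related or not; open list of four examples; no seriousness criterion |
| Ascertainment | Same paragraph; Procedures | Participant report; no event questions described |
| Analysis | Analysis, Feasibility Outcomes | Adverse events not mentioned |

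The label is narrower than the hypothesis, while the definition beneath it is broader than the label. An uninfected reopened ulcer managed in clinic, or a fall treated at home, is neither clearly in nor clearly out.

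**Exposure.** The target is given as follows: "The ability to meet recruitment targets (20 participants per group, 40 total) was assessed". Classes run three times a week for 12 weeks, so 3 × 12 = 36 sessions each, and 20 × 36 = 720 possible attendances in the exercise arm. No exercise-type event is named for any of them.

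**Denominator for wound enlargement.** The share h healed at entry is not given; take 0, 25, 50 and 75%. Assume that only those with an open wound at entry are at risk, so n = 20 × (1 − h). With zero events, the exact one-sided 95% upper limit on the risk is 1 − 0.05^(1/n).

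| h | n at risk | Upper limit after 0 events |
|---|---|---|
| 0% | 20 | 13.9% |
| 25% | 15 | 18.1% |
| 50% | 10 | 25.9% |
| 75% | 5 | 45.1% |

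A bare count per arm does not show which row applies.

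**Unnamed ulcer events, upper range.** Assume that 25 to 75% of all 40 participants enter healed (10 to 30 people) and that 5 to 15% of them re-ulcerate within 12 weeks. Neither figure is in the documents. The range is 10 × 0.05 = 0.5 to 30 × 0.15 = 4.5 events over both arms. This is an upper range, because a re-ulceration with infection, or one leading to a hospital or emergency visit, already matches a listed example.

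**What direct questions would yield.** With 20 exercisers asked, the chance of seeing at least one participant with a given event is 1 − (1 − p)^20: 64%, 88% and 99% for an assumed true risk p of 5, 10 and 20%. Even at this size, the questions would be informative.

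**The case against.** The strongest reply is that the definition is wide. It speaks of adverse outcomes whether or not related to the study, and it sets no seriousness test. The list is introduced as examples, so a fall or a reopened ulcer could be counted. On this view the mismatch is one of wording, and one example is missing from an open list.

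Much of this stands, and it rules out three stronger readings that a reader might infer:

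- *That wound enlargement cannot occur in healed participants.* An ulcer that forms or reopens during the 12 weeks could be recorded as an increase, or could then enlarge, and infection can occur in anyone.
- *That events are collected only if they lead to a hospital or emergency visit.* Two of the four examples, wound enlargement and infection, need no such visit.
- *That the hypothesis cannot be tested because non-serious events are missing.* The plan also leaves low undefined, and collecting more event types would not by itself cure that.

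It is also fair to say that no procedure is described for eliciting any event, so ulcer recurrence is no worse placed than infection in that respect. The document, dated July 2022, is in the past tense, so new questions may no longer be possible.

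The reply does not remove the point. A narrow label over an open definition, filled by self-report, leaves inclusion to individual reading. Breadth that nobody is told to apply does not ensure that events are captured.

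**Conclusion.** The point holds in a limited form. The count of events labelled serious does not support a conclusion about adverse events in general, because the plan does not establish which other events were asked about or counted. The wound examples fit participants with an open ulcer better than those healed at entry. The documents do not show that such events were missed, only that their capture is left to interpretation.

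The mismatch rests on the text alone. Its size rests on assumptions. The rise in the upper limit from 13.9% to 25.9% needs half of the exercise arm to be healed at entry and no wound enlargement among the rest. The 0.5 to 4.5 unnamed ulcer events are an assumption-based upper range, not an estimate. The issue limits the safety claim; it does not affect the randomised comparison of health outcomes.

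**What to change.** If data can still be collected:

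1. Add new or reopened ulcer to the listed events under Outcomes (Feasibility Outcomes).
2. Ask both arms the same short set of questions, at the existing regular contacts or in the 12-week survey: any fall, any low blood sugar episode, any injury or pain that limited activity, any new or reopened ulcer.
3. Report the answers by arm, separately from serious adverse events, giving the number of participants affected as well as the number of events, and split by ulcer status at entry.
4. Base any statement about the frequency of adverse events on that table.

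If collection is complete, limit the hypothesis in the Aim of study and the safety conclusion to serious adverse events as the plan defines them, and state that other adverse events were not systematically collected.

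The first route costs a few questions and one table, and the reported event frequency will be higher. The second costs a change of wording and a narrower claim.

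### Ulcer status at entry (current or recently healed) enters neither the allocation nor the outcome models nor the adverse-event counts, so a chance imbalance could mislead the wound-event comparison and, under a further assumption, the health-outcome contrasts

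*Combined protocol and SAP*

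**What the plan says.** The combined protocol and SAP accepts, under Participants, people with "current or recently-healed DFU (in the last six months", and gives no quota or expected split between the two states. On allocation the same section says "A randomization schedule was created using random number generator in Microsoft Excel", and that the coordinator "created the randomization schedule for 40 potential participants prior to any study enrollment". It mentions no stratification, blocking or minimisation. The Analysis section gives "recruitment targets (20 participants per group, 40 total" as the targets.

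For health outcomes, the Analysis section states "The ANOVA models included two factors, each with two levels", namely group and time. The effect is read from "Significant interactions of group x time". Alpha is 0.10 "for health outcomes and was not adjusted for multiple comparisons".

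Under Feasibility Outcomes, SAEs are events "such as hospitalizations, emergency room visits, increase in wound size" and infection, summarised as one total per arm. No denominator of people at risk is given, and there is no breakdown by ulcer status.

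Participant characteristics are compared between arms, with age, sex, body-mass index and duration of diabetes as examples. Ulcer status is not named, although the list is open. No adjustment follows from that comparison, whatever it shows.

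**The concern.** The two eligible states differ in ways that matter to the outcomes. A wound can enlarge only if there is one, so a participant with a healed ulcer must first re-ulcerate before that event can occur. If one arm starts with more open ulcers, a raw count of wound events will tend to be higher there even if exercise has no effect. Depending on the direction, exercise could look harmful or a real harm could be hidden. SAEs are one of four feasibility parameters, and a low frequency of adverse events is a stated hypothesis, so readers will compare these counts.

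The aim statement also links weight-bearing restrictions to wound-healing protocols. If wounds close and restrictions lift during the 12 weeks, sit-to-stand, timed-up-and-go and physical function may change differently in those who entered with an open ulcer. An imbalance would then move the group x time estimates, which the plan says could be used to power and inform a larger RCT.

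**Working it through.** **Inputs from the document:** 40 participants, target 20 per arm; two-factor ANOVA read through group x time; alpha 0.10, taken as two-sided; SAEs as totals per arm. The sample size has no stated derivation (no effect size, SD or power), so there is no planned figure to reproduce.

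**Inputs assumed, because the document gives none:** current-ulcer share 30-70%; difference in 12-week change between current and healed ulcers, g = 0.25-1.0 SD; wound-event rates by ulcer status as stated in step 2.

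**1. How large an imbalance could chance produce?**

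Under a fixed 20/20 split, the number k of current ulcers in one arm is hypergeometric (40 people, C with a current ulcer, 20 drawn). The gap in share is |2k - C|/20. Under simple randomisation each person is allocated independently; those figures come from simulation.

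| Current-ulcer share | Allocation | P(gap of 20 points or more) | P(gap of 30 points or more) |
|---|---|---|---|
| 50% (C = 20) | fixed 20/20 | 34% | 11% |
| 30% or 70% (C = 12 or 28) | fixed 20/20 | 30% | 8% |
| 50% | simple | 27% | 8% |
| 30% or 70% | simple | 19% | 4.5% |

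The document does not say whether the Excel list forced equal arms, so both cases are shown.

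**2. Wound events with no exercise effect**

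The expected count per arm is (current ulcers x rate if current) + (healed x rate if healed).

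- Only current ulcers at risk, 12 against 8: ratio 12/8 = 1.50. With 13 against 7: 13/7 = 1.86.
- Assumed rates 20% (current) and 2% (healed), 12 against 8: 12 x 0.20 + 8 x 0.02 = 2.56, against 8 x 0.20 + 12 x 0.02 = 1.84; ratio 1.39. With 13 against 7: 2.74 against 1.66; ratio 1.65.

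**3. Health outcomes**

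With two time points, group x time tests the difference between arms in mean change. A fixed difference in level between current and healed ulcers cancels. If change differs by g, the contrast in the realised trial shifts by gap x g. For a 20-point gap:

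- g = 0.25: 0.20 x 0.25 = 0.05 SD
- g = 0.5: 0.10 SD
- g = 0.8: 0.16 SD
- g = 1.0: 0.20 SD

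For scale, the standard error of the contrast is about sqrt(2/20) = 0.32 SD. Allowing for the extra variance from g in the unadjusted model, SE = 0.316 x sqrt(1 + 0.24g²), where 0.24 = 0.6 x 0.4. By normal approximation, the false-positive risk given a 20-point gap is 0.104, 0.116 and 0.137 for g = 0.25, 0.5 and 0.8, against a nominal 0.10. Given a 30-point gap it is 0.109, 0.136 and 0.183.

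Over all possible allocations the error rate does not move. In 10,000 simulated trials (20/20 split, half with a current ulcer), type I error without and with adjustment was 0.102 and 0.102 at g = 0.5, and 0.099 and 0.100 at g = 0.8.

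**4. Precision gained by adjusting**

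At a 50/50 mix, the share of variance in change explained by ulcer status is 0.25g²/(1 + 0.25g²).

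- g = 0.25: 0.0156/1.0156 = 1.5%
- g = 0.5: 0.0625/1.0625 = 5.9%
- g = 1.0: 0.25/1.25 = 20%

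**The case against.** Several objections stand and limit the point.

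- A reader might infer that weight-bearing restrictions by themselves distort the function results. They bear on level, and level cancels in group x time. The document gives no figure for a difference in change.
- A reader might infer that a material imbalance is likely. A gap of 20 points or more has a probability of 19-34% under the assumed mixes, so it is possible rather than expected.
- A reader might infer that the design is biased. Randomisation leaves the estimate unbiased on average, and overall type I error holds. What remains is a shift in the realised trial if the arms happen to differ, and some lost precision.
- That ulcer status is already on file as a separate variable is an inference. The eligibility check must establish it, but the document states one either/or criterion and does not say the two states are recorded separately. Status may also be among the baseline characteristics compared, since that list is open.
- Wound enlargement is one example among several SAEs. Hospitalisation, emergency visits and infection do not require an ulcer at entry. No formal SAE test is planned.
- The text is in the past tense, so stratifying this trial's allocation is probably no longer possible, and a covariate added now may be post hoc.

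None of this answers the core: whatever is recorded, no described model or count uses ulcer status, and a raw count of wound enlargement carries no information on how many had a wound to enlarge.

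**Conclusion.** The point holds as a moderate, inexpensive improvement to a pilot trial. The safety part is the stronger: with 12 against 8 current ulcers, wound-enlargement counts would be expected to differ by a ratio of up to 1.5 with no treatment effect. It needs only that an imbalance occurs and that the event is more frequent in people who enter with an open ulcer. The harm is to the interpretation of a descriptive comparison.

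The health-outcome part is conditional on 12-week change differing by ulcer status. The resulting shift of 0.05-0.20 SD at a 20-point gap is small to moderate against a standard error of about 0.32 SD, and the precision gain of 1.5-20% rests on the same assumption. The documents do not support a claim that the function results are invalid or that the error rate is inflated overall.

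**What to change.** 1. Report ulcer status at entry (current or healed) by arm.
2. Report wound enlargement with the number at risk: participants with an open ulcer at entry or at any time during the 12 weeks, so that re-ulceration is not lost. Re-ulceration happens after randomisation, so show those participants as a separate part of the denominator. Alongside, report total SAEs by ulcer status at entry.
3. Add ulcer status and its interaction with time to each health-outcome model. The interaction is essential: a main effect alone leaves group x time unchanged. If data have already been seen, label this a sensitivity analysis and keep the two-factor ANOVA as the planned one.
4. For the larger RCT only, stratify allocation by ulcer status.

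Cost: about 1 degree of freedom of about 38 (40 participants less 2 arms) and a little extra reporting. If the two states were not recorded separately, status would have to be recovered from the eligibility records.

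### The plan does not require the baseline survey and performance tests to be finished before the allocation envelope is opened, and its two accounts of enrolment, consent and baseline do not give one order

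*Combined protocol and SAP*

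**What the plan says.** Materials and methods, Participants, describes entry to the trial: "Interested patients were screened by telephone for initial eligibility and, if eligible to participate, were enrolled and randomized" to one of the two groups. On concealment it says: "Group assignment was placed in sealed envelopes to blind study investigators to randomization allocation". On when the envelope is opened: "Corresponding envelopes were not opened until the participant was enrolled into the study". The section closes with a general statement on consent: "Informed consent was obtained from all participants prior to their involvement in the study".

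Procedures, Baseline data collection session, describes the first visit: "At the baseline session, a study investigator explained the study to participants and obtained informed consent". The next sentence is: "We then administered a baseline survey and obtained performance measurements". The 5xSTS, TUG and biceps curls follow the survey, and the HbA1c blood draw comes last, at a hospital laboratory.

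Analysis, Health Outcomes, uses these baseline values as one level of the time factor in a two-by-two repeated measures ANOVA ("group: intervention, control; time: pre-intervention, post-intervention"). The benefit of exercise is judged by the group x time interaction, at alpha 0.10 without adjustment for multiplicity.

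**The concern.** The two sections do not share one sequence, and neither ties the opening of the envelope to completion of the baseline measures. The sealed envelopes conceal the arm up to enrolment. They do not protect measurements taken after it.

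This matters because every health outcome is analysed as a difference in change from baseline. Someone who already knows their arm may answer a questionnaire or perform a timed test differently, and a tester who knows it may encourage differently. Most of the outcomes are exposed: the PROMIS measures and balance confidence are self-reported, and 5xSTS, TUG and biceps curls depend on effort. HbA1c is neither, so little of the concern applies to it.

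On the literal order there is a second consequence. A person who learns the arm and then does not attend the baseline session leaves no baseline data. Under Outcomes, Feasibility Outcomes, that person counts as a non-completer. The planned comparison of completers with non-completers relies on pre-intervention characteristics, and those collected at the baseline session would be missing for exactly these people.

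**Working it through.** The plan states no figure on this point, so there is nothing to reproduce. The check compares the order of events and then works out what a shifted baseline would do to the planned test.

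**Step 1. Order of events under each reading of the word enrolled**

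| Reading | Order that results | Must baseline be complete before the arm is known? |
|---|---|---|
| (a) Enrolled after the telephone screen, as Participants literally reads | Telephone screen, enrolment and randomisation, then consent, survey and tests at the visit | No: the arm may be known before consent and before all baseline measures |
| (b) Enrolled means consented at the baseline visit | Telephone screen, consent and enrolment at the visit, with the envelope permitted from that moment; survey and tests also follow consent | No: the order of envelope and measurements is left open |

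The envelope rule sets an earliest moment, not a latest one. Under (b) the envelope could have been opened after the tests, but the plan does not require it. No section describes a baseline assessor or a participant who is unaware of the arm.

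**Step 2. Effect of a shifted baseline on the estimate**

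With E for exercise and C for control, the interaction estimate is

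(post_E − pre_E) − (post_C − pre_C).

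If knowledge of the arm moves pre_E by b and nothing else changes, the estimate moves by −b. For example, with an assumed b of 1 s, an exercise-arm 5xSTS that is 1 s slower at baseline for this reason alone appears as a 1 s improvement.

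**Step 3. Illustration of the false-positive rate**

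From the plan: 20 per group and alpha 0.10. Assumptions, not in the documents: a two-sided test, no true effect, equal SD at both times, a baseline shift of b SD in the exercise arm, and pre-post correlation r.

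- The group x time test is equivalent to a t-test on change scores, with df = 2 × 20 − 2 = 38.
- SD of change, in units of the outcome SD: √(2(1 − r)).
- Noncentrality: b / √(2(1 − r)) × √(20/2).
- Example: b = 0.2 and r = 0.8 give 0.2 / 0.632 × 3.162 = 1.0.

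Two-sided rejection rates from the noncentral t distribution:

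| b (SD) | r = 0.5 | r = 0.7 | r = 0.8 |
|---|---|---|---|
| 0 | 0.100 | 0.100 | 0.100 |
| 0.1 | 0.116 | 0.127 | 0.141 |
| 0.2 | 0.165 | 0.207 | 0.258 |
| 0.3 | 0.243 | 0.331 | 0.433 |

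**Step 4. Losses between allocation and baseline, reading (a) only**

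Each person lost is 1/20 = 5% of an arm. An assumed 2 to 4 losses would be 2/20 = 10% to 4/20 = 20%.

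**Step 5. Eligibility that is not settled before allocation**

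The cognitive screen is an exclusion criterion with no stated time. If it is given at the visit after the envelope is opened, it becomes a post-randomisation exclusion. A physician's request that the patient not exercise is also an exclusion, and the letter that prompts it goes only to physicians of people already allocated to exercise. As written, that criterion is prompted after allocation and in one arm.

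**The case against.** The strongest reply is that the sequence is unclear, not wrong. The telephone call settles only initial eligibility, no date or place is given for enrolment, and the general statement puts consent before involvement. If enrolment happens at the visit, all the consent statements agree, nobody is randomised before consenting, and refusal between allocation and consent cannot occur. This stands. A reader might infer that people were randomised before consent, or that baseline was measured with the arm known. The documents support neither as fact: the first is one reading of Participants, and the second is something the plan fails to exclude. What the reply does not remove is the gap within the visit, which remains on both readings.

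The sizes are also hypothetical. No document figure shows that a shift occurred, how large it was or in which direction. This stands too; Steps 3 and 4 show only sensitivity.

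The stated aim is feasibility, and adherence, satisfaction and serious adverse event counts do not use the baseline health measures. Health outcomes are tested at a lenient alpha, and participants know their arm at 12 weeks whatever is done at baseline. All of this is true and limits the weight of the point; a better order at entry does nothing for bias at follow-up. But the plan intends the health results, if favourable, to power and inform a larger trial, so an avoidable bias at baseline would carry forward.

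Finally, one might want enrolment defined as fully eligible before the envelope is opened. That does not work while the physician response is sought after allocation in the exercise arm only. This objection is right, and the fix takes account of it.

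**Conclusion.** The point holds as a fault in the stated order. Participants and Baseline data collection session must be reconciled, and on either reading the envelope may be opened before the survey, 5xSTS, TUG and biceps curls. This is more than a missing detail, because the only stated condition for opening is enrolment, which protects the baseline less than a rule tied to completed testing would.

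The one-for-one transfer of a baseline shift into the group x time estimate is algebra and needs no assumption beyond the shift itself. The false-positive rates rest on the assumed b and r: 0.116 to 0.141 at 0.1 SD, and 0.243 to 0.433 at 0.3 SD, against a nominal 0.10. They do not estimate what happened in this trial. Confidence is high that the order is not secured. The documents give no basis for saying that the baseline was in fact biased.

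**What to change.** State one order in both sections: telephone pre-screen; then, at the baseline session, consent, cognitive screen, baseline survey and performance tests; and only then open the envelope. It need not wait for the laboratory blood draw. Tie opening to consent and completed baseline testing, in place of the undefined term enrolled.

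Reconcile the physician-response exclusion with the randomisation step. As written it cannot be part of eligibility before the envelope is opened. Report anyone excluded this way by arm, and keep them in the randomised count.

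Because the study is described in the past tense, rewording cannot change what was done. State the order actually used and who knew the arm at baseline, and report by arm the number randomised without a baseline. If baseline followed allocation, give this as a limitation of the group x time results. Apply the order above to the larger RCT.

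The cost is small: the same visit, staff and envelopes, with the envelope held until the end of testing. The disclosure needs only a check of enrolment, consent and visit records.
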